## **7.2 Laboratory Procedures/Evaluations**

### **7.2.1**

### **Clinical Laboratory Evaluations**

The following tests will be reviewed for patients who are included in the study but will be performed as standard of care for lung transplant recipients:

- **Hematology:** white blood cells (WBC) collected weekly for the first 3 months and monthly for months 4-12
- **Biochemistry:** potassium and creatinine collected weekly for the first 3 months and monthly for months 4-12
- **Tacrolimus:** C0 levels will be obtained at all routine post-transplant follow-up visits and more frequently as needed for sub- or supra-therapeutic levels collected weekly for the first 3 months and monthly for months 4-12

### **7.2.2** **Control Cohort**

### **Retrospective data to be collected in the Historical**

Specific data pertaining to primary and secondary outcomes to be collected in the Historical Control Cohort is the same as listed above in the Prospective Cohort and at the same time points.

## **7.3 Concomitant Medications, Treatments, and Procedures**

The subjects will receive concomitant medications, which would otherwise be given as standard of care for patients undergoing a lung transplant.

### **7.3.1** **Procedures**

### **Precautionary Medications, Treatments, and**

Treatment with potent CYP3A4 inducers (e.g. rifampin, St. John's Wort, efavirenz, carbamazepine, phenytoin, phenobarbital, etc.) or inhibitors (ritonavir, cobicistat, darunavir, lopinavir, atazanavir, etc.) requires special dosing considerations and potentially more frequent monitoring of tacrolimus C0 levels.

CONFIDENTIAL

This material is the property of the NYU School of Medicine and Langone Medical Center. Do not disclose or use except as authorized in writing by the study sponsor

Management of these significant drug interactions will be discussed by the study team and any dose adjustment plan documented.

#### **7.4 Prohibited Medications, Treatments, and Procedures**

As frequent tacrolimus C0 level monitoring is available, no medications will be explicitly prohibited from the study.

#### **7.5 Participant Access to Study Agent at Study Closure**

Patients will be eligible to continue Envarsus XR through standard prescription coverage at completion of the study. The study team will assist with ensuring continuance of therapy is secured. Based on our current experience, Envarsus XR is readily obtainable for lung transplant recipients with the assistance of pharmacy liaisons who provide prior authorization support. The cost of any copayment for Envarsus XR past the one year study window would be the responsibility of the patient. If insurance coverage of Envarsus XR is not able to be obtained, the patient would then be converted back to IR tacrolimus at the discretion of the treating transplant pulmonologist, who would also be a study team member.

### **8 Assessment of Safety**

#### **8.1 Specification of Safety Parameters**

##### **8.1.1**

##### **Definition of Adverse Events (AE)**

An **adverse event** (AE) is any symptom, sign, illness or experience that develops or worsens in severity during the course of the study. Intercurrent illnesses or injuries should be regarded as adverse events. Abnormal results of diagnostic procedures are considered to be adverse events if the abnormality:

- results in study withdrawal
- is associated with a serious adverse event
- is associated with clinical signs or symptoms
- leads to additional treatment or to further diagnostic tests
- is considered by the investigator to be of clinical significance

##### **8.1.2**

##### **Definition of Serious Adverse Events (SAE)**

###### **Serious Adverse Event**

Adverse events are classified as serious or non-serious. A **serious adverse event** is any AE that is:

- fatal
- life-threatening
- requires or prolongs hospital stay
- results in persistent or significant disability or incapacity
- a congenital anomaly or birth defect
- an important medical event

Important medical events are those that may not be immediately life threatening, but are clearly of major clinical significance. They may jeopardize the subject, and may require intervention to prevent one of the other serious outcomes noted above. For example, drug overdose or abuse, a seizure that did not result in in-patient hospitalization, or intensive treatment of bronchospasm in an emergency department would typically be considered serious.

All adverse events that do not meet any of the criteria for serious should be regarded as **non-serious adverse events**.

CONFIDENTIAL

This material is the property of the NYU School of Medicine and Langone Medical Center. Do not disclose or use except as authorized in writing by the study sponsor

## 8.1.3

## Definition of Unanticipated Problems (UP)

### Unanticipated Problems Involving Risk to Subjects or Others

Any incident, experience, or outcome that meets all of the following criteria:

- Unexpected in nature, severity, or frequency (i.e. not described in study-related documents such as the IRB-approved protocol or consent form, the investigators brochure, etc)
- Related or possibly related to participation in the research (i.e. possibly related means there is a reasonable possibility that the incident experience, or outcome may have been caused by the procedures involved in the research)
- Suggests that the research places subjects or others at greater risk of harm (including physical, psychological, economic, or social harm).

## 8.2 Classification of an Adverse Event

### 8.2.1

### Severity of Event

For AEs not included in the protocol defined grading system, the following guidelines will be used to describe severity.

- **Mild** – Events require minimal or no treatment and do not interfere with the participant's daily activities.
- **Moderate** – Events result in a low level of inconvenience or concern with the therapeutic measures. Moderate events may cause some interference with functioning.
- **Severe** – Events interrupt a participant's usual daily activity and may require systemic drug therapy or other treatment. Severe events are usually potentially life-threatening or incapacitating.

### 8.2.2

### Relationship to Study Agent

The clinician's assessment of an AE's relationship to study drug is part of the documentation process, but it is not a factor in determining what is or is not reported in the study. If there is any doubt as to whether a clinical observation is an AE, the event should be reported. All AEs must have their relationship to study agent assessed. In a clinical trial, the study product must always be suspect. To help assess, the following guidelines are used.

- **Related** – The AE is known to occur with the study agent, there is a reasonable possibility that the study agent caused the AE, or there is a temporal relationship between the study agent and event. Reasonable possibility means that there is evidence to suggest a causal relationship between the study agent and the AE.
- **Not Related** – There is not a reasonable possibility that the administration of the study agent caused the event, there is no temporal relationship between the study agent and event onset, or an alternate etiology has been established.

For all collected AEs, the clinician who examines and evaluates the participant will determine the AE's causality based on temporal relationship and his/her clinical judgment. The degree of certainty about causality will be graded using the categories below.

- **Definitely Related** – There is clear evidence to suggest a causal relationship, and other possible contributing factors can be ruled out. The clinical event, including an abnormal laboratory test result, occurs in a plausible time relationship to drug administration and cannot be explained by concurrent disease or other drugs or chemicals. The response to withdrawal of the drug (dechallenge) should be clinically plausible. The event must be pharmacologically or phenomenologically definitive, with use of a satisfactory rechallenge procedure if necessary.
- **Probably Related** – There is evidence to suggest a causal relationship, and the influence of other factors is unlikely. The clinical event, including an abnormal laboratory test result, occurs within a reasonable time after administration of the drug, is unlikely to be attributed to concurrent disease

CONFIDENTIAL

This material is the property of the NYU School of Medicine and Langone Medical Center. Do not disclose or use except as authorized in writing by the study sponsor

or other drugs or chemicals, and follows a clinically reasonable response on withdrawal (dechallenge). Rechallenge information is not required to fulfill this definition.

- **Possibly Related** – There is some evidence to suggest a causal relationship (e.g., the event occurred within a reasonable time after administration of the trial medication). However, other factors may have contributed to the event (e.g., the participant's clinical condition, other concomitant events). Although an AE may rate only as "possibly related" soon after discovery, it can be flagged as requiring more information and later be upgraded to "probably related" or "definitely related," as appropriate.
- **Unlikely to be related** – A clinical event, including an abnormal laboratory test result, whose temporal relationship to drug administration makes a causal relationship improbable (e.g., the event did not occur within a reasonable time after administration of the trial medication) and in which other drugs or chemicals or underlying disease provides plausible explanations (e.g., the participant's clinical condition, other concomitant treatments).
- **Not Related** – The AE is completely independent of study drug administration, and/or evidence exists that the event is definitely related to another etiology. There must be an alternative, definitive etiology documented by the clinician.

### 8.2.3

### Expectedness

The Principal Investigator will be responsible for determining whether an AE is expected or unexpected. An AE will be considered unexpected if the nature, severity, or frequency of the event is not consistent with the risk information previously described for the study agent.

## 8.3 Time Period and Frequency for Event Assessment and Follow-Up

The occurrence of an AE or SAE may come to the attention of study personnel during study visits and interviews of a study participant presenting for medical care, or upon review by a study monitor. All AEs including local and systemic reactions not meeting the criteria for SAEs will be captured on the appropriate RF. Information to be collected includes event description, time of onset, clinician's assessment of severity, relationship to study product (assessed only by those with the training and authority to make a diagnosis), and time of resolution/stabilization of the event. All AEs occurring while on study must be documented appropriately regardless of relationship. All AEs will be followed to adequate resolution.

Any medical condition that is present at the time that the participant is screened will be considered as baseline and not reported as an AE. However, if the study participant's condition deteriorates at any time during the study, it will be recorded as an AE. UPs will be recorded in the data collection system throughout the study.

Changes in the severity of an AE will be documented to allow an assessment of the duration of the event at each level of severity to be performed. AEs characterized as intermittent require documentation of onset and duration of each episode.

The PI will record all reportable events with start dates occurring any time after informed consent is obtained until 7 (for non-serious AEs) or 30 days (for SAEs) after the last day of study participation. At each study visit, the investigator will inquire about the occurrence of AE/SAEs since the last visit. Events will be followed for outcome information until resolution or stabilization.

All unresolved adverse events should be followed by the investigator until the events are resolved, the subject is lost to follow-up, or the adverse event is otherwise explained. At the last scheduled visit, the investigator should instruct each subject to report any subsequent event(s) that the subject, or the subject's personal physician, believes might reasonably be related to participation in this study. The investigator should notify the study sponsor of any death or adverse event occurring at any time after a subject has discontinued or terminated study participation that may reasonably be related to this study. The sponsor should also be notified if the investigator should become aware of the development of cancer or of a congenital anomaly in a subsequently conceived offspring of a subject that has participated in this study.

CONFIDENTIAL

This material is the property of the NYU School of Medicine and Langone Medical Center. Do not disclose or use except as authorized in writing by the study sponsor

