### **5.7 Participant Withdrawal or Termination**

#### **5.7.1**

#### **Reasons for Withdrawal or Termination**

Participants are free to withdraw from participation in the study at any time upon request. An investigator may terminate participation in the study if:

- Any clinical adverse event (AE), laboratory abnormality, or other medical condition or situation occurs such that continued participation in the study would not be in the best interest of the participant
- The participant meets an exclusion criterion (either newly developed or not previously recognized) that precludes further study participation

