#### **5.7.2 Termination**

#### **Handling of Participant Withdrawals or**

In the event a patient requests to withdrawal or is terminated from the study, the patient will either be continued on Envarsus XR or converted back to IR tacrolimus at the discretion of the transplant pulmonologist. If a patient withdrawals from the trial due to a hypersensitivity or severe adverse reaction to tacrolimus, future anti-rejection regimen will be determined by the transplant pulmonologist.

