## **10.3 Analysis Datasets**

All subjects will be entered into a database containing de-identified information. All patients who take one dose of the study drug will be included in the safety analyses (intention-to-treat). However, only patients completing the full first year post-lung transplant will be included in the efficacy analysis (per-protocol analysis).

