##### **10.4.7.1 Safety Review**

Any patient death will result in halting of any further enrollment in the study and an assessment of whether the death was related to Envarsus XR exposure or complications thereof. Even in the event of a patient death, currently enrolled patients who are actively being treated with Envarsus XR and tolerating therapy will continue to receive therapy so as not to put them at risk for rejection as a consequence of converting therapy. If the patient death is deemed related to Envarsus XR, enrolled patients receiving Envarsus XR will be switched to an alternative therapy including, but not limited to: IR tacrolimus, cyclosporine, sirolimus, everolimus, mycophenolate, belatacept, or some combination thereof.

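### Patients whose study participation ends have no planned outcome follow-up to 1 year, and the completers-only rule in 10.3 can remove them from the efficacy results, including the primary retention percentage

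*Combined protocol and SAP*

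**What the plan says.** Section 5.7.1 lets a patient withdraw on request. It also lets the investigator end participation when an adverse event, laboratory abnormality or other condition means that "continued participation in the study would not be in the best interest of the participant". Section 5.7.2 then says that "the patient will either be continued on Envarsus XR or converted back to IR tacrolimus at the discretion of the transplant pulmonologist". It describes no further data collection.

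Section 8.3 has reportable events recorded from consent "until 7 (for non-serious AEs) or 30 days (for SAEs) after the last day of study participation". It adds two extensions. Open events continue: "All unresolved adverse events should be followed by the investigator until the events are resolved", or the patient is lost to follow-up, or the event is otherwise explained. The sponsor is also to be told of "any death or adverse event occurring at any time after a subject has discontinued or terminated study participation", but only where a relation to the study is reasonable. Section 13.4 asks for at least vital status at the end of the scheduled period, and only for patients who revoke authorization to use their health information.

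Section 10.3 puts everyone who took a dose in the safety analyses and restricts efficacy to patients who complete the full first post-transplant year. Section 10.4.2, headed as the analysis of the primary efficacy endpoint, covers the percentage still on Envarsus XR at 1 year. Section 10.4.4 makes discontinuation of therapy and worsening kidney disease safety endpoints. The historical controls (5.1) must have completed one year on IR tacrolimus.

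**The concern.** The primary objective is feasibility, so the patients who fail or do not tolerate Envarsus XR are the most informative ones. The protocol itself treats conversion as carrying a rejection risk. In 10.4.7.1, patients tolerating the drug stay on it after another patient's death "so as not to put them at risk for rejection as a consequence of converting therapy". That sentence concerns a halt in enrolment and not individual withdrawals, but it shows which outcome matters after a switch.

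For a patient whose participation is ended, no passage directs the team to go on collecting biopsy grades, treated rejection, DSA, creatinine, C0 or survival to 1 year. The analysis rule then excludes that patient from efficacy. What is at stake is a retention figure without its failures in the denominator, and one-year outcomes described only for those who stayed.

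**Working it through.** The plan states no power, dropout rate or expected retention, so it offers no figure to reproduce. The check traces a leaver through the text and then sizes two consequences.

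**1. Two patients side by side.** Patient A stops Envarsus XR but stays in the study. The 8.3 clock has not started, the 7.1.2 data continue, and A can still complete the first year under 10.3. Patient B is terminated under 5.7.1. The clock starts that day, 5.7.2 names the next drug, and 10.3 removes B from efficacy. The protocol never says whether a patient who stops the drug is an A or a B.

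**2. How much of B's remaining year the event window covers.** Inputs: 7 and 30 days (8.3) and a last visit at week 52, day 364 (section 20). The exit day *d* is assumed. Share = window / (364 − *d*).

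| Exit day (assumed) | Days left | New SAEs | New non-serious AEs |
|---|---|---|---|
| 84 | 280 | 30/280 = 10.7% | 7/280 = 2.5% |
| 168 | 196 | 30/196 = 15.3% | 7/196 = 3.6% |
| 252 | 112 | 30/112 = 26.8% | 7/112 = 6.3% |

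These shares concern active recording of new events only. They do not measure missed rejection, which is collected as an outcome from biopsies and treatment records.

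**3. The retention denominator.** Inputs: 40 patients (5.6), all assumed to take a dose; *k* leavers, assumed; everyone else assumed still on Envarsus XR; leavers counted as not retained. All dosed: (40 − *k*)/40. Completers, reading 10.3 literally: (40 − *k*)/(40 − *k*). Intervals are exact 95% (Clopper-Pearson).

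| *k* | All dosed | Completers only |
|---|---|---|
| 2 | 38/40 = 95% (83 to 99) | 38/38 = 100% (91 to 100) |
| 4 | 36/40 = 90% (76 to 97) | 36/36 = 100% (90 to 100) |
| 8 | 32/40 = 80% (64 to 91) | 32/32 = 100% (89 to 100) |
| 12 | 28/40 = 70% (53 to 83) | 28/28 = 100% (88 to 100) |

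Because 5.7.2 lets a leaver remain on Envarsus XR, a leaver's true status at 1 year could be either. Without later data, the all-dosed figure for *k* = 4 could lie anywhere from 36/40 = 90% to 40/40 = 100%, and for *k* = 8 from 80% to 100%. Follow-up from records would settle it.

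**4. Secondary outcomes.** Sections 4.2.2 and 10.4.3 compare ACR, CRSS, treated rejection, CLAD, DSA and survival at 1 year. Taken literally, 10.3 leaves survival with no deaths in the Envarsus XR arm, since a patient who dies in the first year has not completed it. The control criterion in 5.1 does the same to the controls. Both arms are therefore selected on completion.

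**The case against.** The strongest reply is that the clock in 8.3 runs from the end of participation and not from the last dose. Nothing says that stopping Envarsus XR ends participation. A primary endpoint counting who remains on the drug, and a safety endpoint counting discontinuations, both make sense if patients who stop are still followed. Rejection comes from standard-of-care biopsies and treatment records (7.1.2), entered from the electronic record (14.1), so the adverse event window does not govern it. Treating pulmonologists at this single centre belong to the study team (2.2.3, 7.5) and would probably learn of later events.

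Much of this stands. A reader might infer that everyone converted back to IR tacrolimus is followed for only 7 or 30 days, or that failures vanish from the dataset. The text supports neither: the window applies to those whose participation ends, open events are followed further, and every dosed patient stays in the safety set. Three further inferences should not be drawn:

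- The subtherapeutic levels in 2.1 arose on conversion to Envarsus XR, so they say nothing about conversion back.
- Conversion at study closure (7.5) comes after the study year and cannot affect 1-year outcomes.
- Setting the biopsy calendar against the event window does not measure bias, because that window does not control biopsy data.

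The reply does not supply an instruction to collect outcomes after withdrawal or termination. The late-event route is passive and depends on a relatedness judgement, which rejection arising on another product may not pass. The reply also leaves the restriction in 10.3 untouched.

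**Conclusion.** The point holds for patients whose participation ends. Their later ACR, treated rejection, DSA, eGFR and survival are not systematically collected, and 10.3 leaves them out of efficacy. Membership of the safety set does not fill that gap, since it creates no data after exit.

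The size depends on how many leave, which the plan does not state. Each leaver is 1/40 = 2.5 percentage points of the arm. Four or eight assumed exits separate 90% or 80% from 100% on the primary endpoint. This rests on reading the heading of 10.4.2 together with 10.3 literally; a looser reading would keep all 40 in the denominator, and the text should say which is meant.

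A reader might conclude that the Envarsus XR arm will look better than it is against the controls. The documents do not establish that. The controls are also restricted to one-year completers, so the direction of any between-arm bias is undetermined. This is a cheap improvement worth making and does not invalidate the study.

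**What to change.** - **5.7:** define stopping Envarsus XR and withdrawing consent for follow-up as separate events, each with its own date and reason.
- **5.7.2 and 8.3:** state that every patient who took a dose stays in record-based follow-up to 1 year post-transplant unless consent for record use is withdrawn. Collect SAEs, biopsy grades, treated rejection, DSA, creatinine, C0 and vital status from standard-of-care records.
- **10.3 and 10.4.2:** make all dosed patients the denominator of the primary endpoint and include them in the 1-year outcome analyses. Keep completers-only as a sensitivity analysis. State how a patient who leaves the study but stays on Envarsus XR is counted.
- **10.4.4:** report events after conversion back as a separate line.

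The cost is protocol wording and a little more chart abstraction for the patients who stop. No visit, test or treatment rule changes: the source data are routine care at one centre, and retrospective abstraction is already planned (7.2.2, 14.1). One limit remains. With controls still selected as completers, the all-dosed comparison is not like for like, so the report should say so and show the completers-only result beside it.
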